7.1.2 STANDARD-OF-CARE STUDY PROCEDURES

All Investigators are to provide appropriate care to their subjects as they deem necessary; however, additional standard-of-care study procedures are not required by this protocol.

7.2 LABORATORY PROCEDURES/EVALUATIONS

7.2.1 CLINICAL LABORATORY EVALUATIONS

Specimens for clinical laboratory analysis by the central laboratory will be collected by a qualified staff member at Visit 2E, Visit 3E, every 52 weeks thereafter (e.g., Visits 6E, 8E, etc.), and at the Termination Visit. Subjects should fast prior to the Visit 3E clinical laboratory collection. Refer to the Laboratory Manual for details about collection of specimens. At a minimum, the following tests will be conducted:

- **Chemistry panel:** Albumin, alkaline phosphatase (ALP), alanine aminotransferase (ALT), aspartate aminotransferase (AST), blood urea nitrogen, bicarbonate, calcium, calcium (corrected total), chloride, creatinine, glucose, lactate dehydrogenase (LDH), potassium, sodium, bilirubin (total)
- **Hematology:** Hemoglobin, hematocrit, red blood cell (RBC) count, white blood cell (WBC) count with differential, and platelet count
- **Urinalysis:** Clarity, specific gravity, pH, protein, glucose, ketones, nitrite, leukocyte esterase, and occult blood

Urine microscopy will be performed if urinalysis urine protein, leukocyte esterase (WBC esterase), occult blood, or nitrite values are out of range, or if the Investigator deems that the microscopy is clinically warranted.

The results of the clinical laboratory tests will be reported on the laboratory's standard reports. The Investigator must review all laboratory reports in a timely manner, noting "not clinically significant" (NCS) or comment on the clinical significance of any result that is outside the normal range for the laboratory, then date and initial the report. The Investigator must report all laboratory results that are BOTH outside the normal range for the laboratory AND, in the opinion of the Investigator, clinically significant. If any abnormal, clinically significant laboratory measure is found, it should be reported as an AE.

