7.3.2 STUDY VISITS

Visit 2E

Visit 2E should occur 24 weeks after the Visit 1E injection with a window of \pm 4 weeks.

Confidential

The following procedures and assessments will be performed at Visit 2E:

- Pain NRS assessment
- WOMAC questionnaire
- Collection of AE and concomitant procedures/therapies/medication data
- Assessment of NSAID/acetaminophen usage
- Knee examination
- Weight measurement
- Vital sign measurements (pulse rate and blood pressure)
- Venipuncture and collection of samples for clinical laboratory tests
- Radiograph – bilateral in weight-bearing fixed flexion position, PA view X-ray

Visit 3E

Visit 3E should occur 48 weeks after the Visit 1E injection with a window of ± 4 weeks. Subjects should fast for 8 hours prior to this visit.

The following procedures and assessments will be performed at Visit 3E:

- Pain NRS assessment
- WOMAC questionnaire
- PASS assessment
- SF-36
- Collection of AE and concomitant procedures/therapies/medication data
- Assessment of NSAID/acetaminophen usage
- Pregnancy test (urine-based) in WOCBP
- Physical examination
- Knee examination
- Weight measurement
- Vital sign measurements (temperature, pulse rate, and blood pressure)
- Venipuncture and collection of samples for clinical laboratory tests and biomarkers
- Radiograph – bilateral in weight-bearing fixed flexion position, PA view X-ray
- IA injection of LOR into the target knee; **the target knee must be the same as the knee injected in the parent study.**

Visit 4E (Phone Visit)

The Visit 4E phone visit should occur on Week 52 (with a window of ± 7 days). Sites will contact subjects to collect AE and concomitant procedures/therapies/medication data.

Visit 5E, 7E, 9E, etc.

These visits should occur on Weeks 74, 126, 178, etc. with a window of ± 4 weeks.

The following procedures and assessments will be performed at these visits:

- Pain NRS assessment
- WOMAC questionnaire
- Collection of AE and concomitant procedures/therapies/medication data
- Assessment of NSAID/acetaminophen usage
- Knee examination
- Radiograph – bilateral in weight-bearing fixed flexion position, PA view X-ray

Visit 6E, 8E, 10E, etc.

These visits should occur on Weeks 100, 152, 204, etc. with a window of ± 4 weeks.

The following procedures and assessments will be performed at these visits:

- Pain NRS assessment
- WOMAC questionnaire
- PASS assessment
- SF-36
- Collection of AE and concomitant procedures/therapies/medication data

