10.4.2 ANALYSIS OF SAFETY ENDPOINT(S)

Safety analyses will be performed on subjects who receive a study injection. Safety assessments include physical examinations, vital signs, clinical laboratory tests, solicitation of AEs and concomitant medications, and general medical evaluations. No formal statistical analyses are planned. Safety will be evaluated based on the incidence, seriousness, severity, and relationship of AEs and by changes in clinical laboratory parameters and vital signs, relative to parent-study baseline. For subjects who cross over from placebo to LOR, subsequent changes in laboratory parameters and vital signs will be relative to Visit 3E.

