10.4.4 BASELINE DESCRIPTIVE STATISTICS

Baseline is defined as the last value recorded before a study injection of the parent study (i.e., parent-study baseline). Baseline descriptive statistics from parent study will include age, sex, race, height, weight, body mass index (BMI), mJSW, Kellgren-Lawrence (KL) grade, and the presence of symptomatic and radiographic OA.

For subjects who cross over from placebo to LOR, Visit 3E (i.e., first exposure to LOR) will serve as an additional reference point for analysis.

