Exclusion criterion #8 (regarding men who are sexually active and of reproductive potential) was deleted.	Sections 1.1 and 5.2	Male contraception requirements were removed to align with PK studies demonstrating no detectable systemic exposure following IA injection of LOR.

Protocol SM04690-OA-07
Biosplice Therapeutics, Inc.

AM02V00
04 May 2021

Change	Sections Affected	Rationale
Estimated subject number and number of sites were edited.	Sections 1.1, 4.1, and 10.5	Change was made for accuracy
Contraception guidelines were revised for WOCBP and removed for men.	Section 5.3.1	Male contraception requirements were removed to align with PK studies demonstrating no detectable systemic exposure following IA injection of LOR.
Instructions for a Total or Partial Knee Replacement Follow-Up were added to the protocol.	Section 5.6.2	Follow-up was added to allow for assessment of TKR/PKR surgery outcomes.
Guidance on study drug injection was updated, including adding a recommendation for aspiration of moderate to large effusions in the target knee prior to injection.	Section 6.1.5	Changes were made to provide further guidance on IA injections.
Accountability procedures were revised.	Section 6.2	Accountability procedures for blinded versus open-label IP were clarified.
Timing of study specific procedures was revised where applicable.	Sections 7.1 and 7.2	Changes were made to align with revised study design.
Fasting requirements for labs was removed (except for Visit 3E).	Section 7.2.1	Change was made as fasting was more relevant to biomarker sample collection.
Study visits and Schedule of Events were revised.	Section 7.3	Changes were made to align with revised study design.
Prohibited procedures were modified.	Section 7.6	Changes were made to refine prohibited procedures.
SAE reporting information and sponsor contact information was updated.	Section 8.4.2	Changes were made to clarify initial SAE reporting and for administrative reasons.
Reporting of pregnancy was limited to pregnant subjects (not pregnant partners of a male subject).	Section 8.4.5	Changes were made to align with removal of male contraception requirements.
Descriptions of statistical methods were updated.	Sections 1.1 and 10.4	Changes were made to align with revised study design.
Medical monitor roles were updated.	Section 15.2	Change was made for administrative reasons.
General editorial/grammatical edits.	Throughout	Changes were made for clarity and accuracy.

Protocol SM04690-OA-07

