7.4.3 Clinical Laboratory Evaluations

Specimens for clinical laboratory analysis were to be collected at Visit 2E, Visit 3E, every 52 weeks thereafter (e.g., Visits 6E, 8E, etc.), and at the Termination Visit. Subjects were asked to fast prior to the Visit 3E clinical laboratory collection. At a minimum, the following tests were conducted:

- **Chemistry panel:** Albumin, alkaline phosphatase (ALP), alanine aminotransferase (ALT), aspartate aminotransferase (AST), blood urea nitrogen, bicarbonate, calcium, calcium (corrected total), chloride, creatinine, glucose, lactate dehydrogenase (LDH), potassium, sodium, bilirubin (total)
- **Hematology:** Hemoglobin, hematocrit, red blood cell (RBC) count, white blood cell (WBC) count with differential, and platelet count
- **Urinalysis:** Clarity, specific gravity, pH, protein, glucose, ketones, nitrite, leukocyte esterase, and occult blood

Urine microscopy was to be performed if urinalysis urine protein, leukocyte esterase (WBC esterase), occult blood, or nitrite values were out of range, or if the Investigator deemed that the microscopy was clinically warranted.

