10.2 Clinical Laboratory Evaluations

All chemistry, hematology and urinalysis results from the central laboratory will be summarized into shift tables as normal, non-clinically significant abnormal, and clinically significant abnormal. Assessments of clinical significance for abnormal values were made by the investigator on results that were outside of the normal range. Shift tables will compare the number and percent of assessments from each visit to baseline values for each treatment group.

All chemistry and hematology results from the central laboratory will be summarized for each treatment group. Descriptive statistics of each laboratory test at all timepoints will be provided along with the change from baseline at each subsequent visit. If a result is below the limit of quantification, it will be set to half the value for analysis (e.g., “< 3” will be analyzed as 1.5). The International System of Units (SI) will be used for all summaries.

Abnormal chemistry, hematology, urinalysis, and urine microscopy results for each subject will be provided in listings that will include laboratory test name, result, normal range, and an explanation for clinically significant values.

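### Fasting is instructed only for the Visit 3E laboratory draw, so placebo-to-LOR subjects' later glucose changes compare an instructed-fasted reference with samples of uncontrolled fasting status

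*Protocol*

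**What the plan says.** **Fasting.** Protocol 7.2.1 states "Subjects should fast prior to the Visit 3E clinical laboratory collection". Protocol 7.3.2 puts a duration on it, under Visit 3E alone: "Subjects should fast for 8 hours prior to this visit". The procedure lists for Visit 2E, for Visits 6E, 8E, 10E and for the Termination Visit, and the schedule in 7.3.4, have no such instruction. SAP 7.4.3 repeats the rule: "Subjects were asked to fast prior to the Visit 3E clinical laboratory collection". The Amendment 02 log indicates that this was deliberate: fasting was dropped at the other laboratory visits because it mattered mainly for the biomarkers.

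**Analyte.** Glucose is in the chemistry panel ("calcium (corrected total), chloride, creatinine, glucose, lactate dehydrogenase (LDH"), and urinalysis includes glucose and ketones.

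**Reference.** Protocol 10.4.2, like the synopsis, says "For subjects who cross over from placebo to LOR, subsequent changes in laboratory parameters and vital signs will be relative to Visit 3E". Protocol 10.4.4 adds that for these subjects "Visit 3E (i.e., first exposure to LOR) will serve as an additional reference point for analysis", so it stands beside parent-study baseline and does not replace it.

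**SAP tables.** SAP 10.2 says "Descriptive statistics of each laboratory test at all timepoints will be provided along with the change from baseline at each subsequent visit" and adds shift tables. It does not say which baseline is meant, and it says nothing about fasting state. SAP 13 does not list dropping the protocol's Visit 3E reference as a change.

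**The concern.** Subjects who received placebo through Visit 3E are the group whose crossover, under Protocol 4.2, is meant to add safety information in people new to LOR. Their pre-exposure laboratory value is the one sample taken under a fasting instruction. Every scheduled sample after it is taken with fasting uncontrolled. Any upward shift in glucose from eating would therefore appear at the point where LOR is first given.

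That period is open-label and has no placebo arm. A reader of the crossover table could take the shift as a safety signal, or could dismiss a real rise as a fasting effect. Nothing in the two documents provides for recording whether a subject had fasted, so the table alone could not settle it.

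**Working it through.** The plan states no figure on this point, so there is none to reproduce. The check sets the sections side by side and then writes down the artefact they imply.

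**1. Sampling condition against role in the analysis, placebo-to-LOR subjects**

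| Draw | Fasting instruction (Protocol 7.2.1, 7.3.2 to 7.3.4) | Role (Protocol 10.4.2, 10.4.4) |
|---|---|---|
| Visit 2E | None in the current text | Before crossover |
| Visit 3E | Yes, 8 hours | Reference for later changes |
| Visits 6E, 8E, etc. | None | Compared with Visit 3E |
| Termination | None | Compared with Visit 3E if after crossover |

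The schedule's footnote makes the injection the last procedure at injection visits, so the Visit 3E draw is a true pre-LOR value. The two conditions differ across exactly that comparison.

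**2. Size of the artefact.** Let p be the share of later samples drawn non-fasted and d the mean non-fasted minus fasted glucose difference. If the Visit 3E samples are fasted, then

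observed mean change = true mean change + p × d.

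If a share q of subjects did not follow the Visit 3E instruction, p becomes p − q. None of p, q or d is in the documents. Taking q = 0 and assuming d of 0.5 to 1.5 mmol/L:

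| p × d (mmol/L) | d = 0.5 | d = 1.0 | d = 1.5 |
|---|---|---|---|
| p = 0.25 | 0.125 | 0.25 | 0.375 |
| p = 0.5 | 0.25 | 0.5 | 0.75 |
| p = 1 | 0.5 | 1.0 | 1.5 |

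**3. Would it be visible?** Assume 200 crossover subjects and an SD of change of 1.1 mmol/L. The standard error is 1.1/√200 = 0.078. At the smallest d (0.5), the artefact is 0.125/0.078 = 1.6, 0.25/0.078 = 3.2 and 0.5/0.078 = 6.4 standard errors for p = 0.25, 0.5 and 1. This only gauges whether it would stand out in a table of means; no test is planned.

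For the share above an upper limit, assume a limit of 6.0, fasted mean 5.3 (SD 0.6) and non-fasted mean 5.8 (SD 1.0). Normal tails give 12.2% fasted and 42.1% non-fasted. Mixing them gives 0.75 × 12.2 + 0.25 × 42.1 = 19.7% at p = 0.25, 27.1% at p = 0.5 and 42.1% at p = 1, all with no drug effect.

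**4. What LOR-LOR subjects add.** They follow the same Visit 3E to Visit 6E schedule and fasting instructions. If p and d are alike in the two groups, p × d cancels in the difference between their changes. What remains is specific to first exposure.

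**5. Can Visit 2E serve as the reference instead?** Amendment 02 is dated 4 May 2021. Going back 24 weeks (168 days) gives 17 November 2020, and the synopsis estimates first consent in August 2020. On those dates, subjects injected between August and mid-November 2020 had a nominal Visit 2E before the fasting requirement was removed. Protocol 13.2 requires IRB approval before an amendment takes effect, so the group could be larger. Visit 2E is therefore not uniformly free of a fasting instruction.

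**The case against.** A reader might infer that every post-exposure glucose change compares a fasted with a non-fasted sample, and that the artefact cannot be told from a drug effect. The documents do not support either step.

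- The absence of an instruction does not make a sample non-fasted. Some subjects will happen to fast, the Visit 3E wording is only a request, and collection details are left to a Laboratory Manual that is not among the documents. This stands, and it is why p is left open.
- Visit 3E is an additional reference, so changes from parent-study baseline remain. This stands, but the fasting state of that baseline is not given either.
- LOR-LOR subjects share the schedule, and SAP 10.2 reports by treatment group, so a common artefact can be separated from a first-exposure effect. This stands, provided that the SAP shows the same Visit 3E to Visit 6E change for both groups, which it does not now specify.
- The SAP may never produce the comparison. Its laboratory endpoint (SAP 3.2.3) is measured from parent-study baseline and ends at Visit 3E, and its named use of a Visit 3E baseline is the concordance analysis (SAP 9.6.4). This stands in part. SAP 10.2 still covers all timepoints against an unnamed baseline, and SAP 13 does not withdraw the protocol's rule.
- The shift tables have three categories, with clinical significance judged by the investigator, and safety is not formally tested. This stands: the share above a limit in the working does not measure the safety endpoint. Descriptive tables are nevertheless how laboratory safety after crossover will be read.

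**Conclusion.** The point holds in a limited form. Both premises are in the text: fasting is instructed at Visit 3E only, and Visit 3E is the protocol's additional reference for later laboratory changes in placebo-to-LOR subjects. Followed as written, the rule adds p × d to their mean glucose change at first LOR exposure.

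On the assumed ranges that is 0.125 to 1.5 mmol/L. It is zero if no later sample is non-fasted or if fasting makes no difference, and smaller than stated if the Visit 3E instruction was not always followed. The size rests wholly on assumptions; the mismatch in sampling condition does not.

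The reach is narrow: descriptive tables for glucose, and by extension urine glucose and ketones. Efficacy is untouched. So is the between-arm comparison at Visit 3E, where both arms had the same instruction. It is worth correcting because the remedy is small.

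**What to change.** **Protocol 7.2.1.** Apply the Visit 3E fasting instruction to the later laboratory draws that are compared with it (Visits 6E, 8E, etc.). Cost: one fasting visit a year for each subject. SAP 4.1 reports administrative termination, with active subjects asked to continue to Visit 6E, so for samples already drawn the remedy lies in the SAP.

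**SAP 10.2.**

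- State which baseline applies to placebo-to-LOR subjects after Visit 3E.
- Tabulate glucose, urine glucose and urine ketones by the fasting instruction in force at the draw, and mark changes from Visit 3E as not matched on fasting.
- Show the same Visit 3E to Visit 6E change for LOR-LOR subjects alongside.
- Do not substitute Visit 2E as the reference by default. Use it only for subjects whose Visit 2E draw carried no fasting instruction, and note that it lies 24 weeks before first LOR exposure.

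Cost: a little extra tabulation for three tests, and the date on which Amendment 02 took effect at each site.

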7.2.2 OTHER ASSAYS OR PROCEDURES

Pregnancy Test

A urine-based pregnancy test will be performed on WOCBP at Visit 1E, Visit 3E, and every 52 weeks thereafter (e.g., Visits 6E, 8E, etc.).

WOCBP are women who are not post-menopausal (defined as 12 months with no menses without an alternative medical cause) or permanently surgically sterile (includes hysterectomy, bilateral salpingectomy, and bilateral oophorectomy).

Biomarkers

Fasting blood samples for biomarker analysis will be collected by a qualified staff member at Visit 3E. Biomarkers that will be assessed include bone biomarkers, P1NP and β -CTX, and a cartilage biomarker, COMP.

7.2.3 SPECIMEN PREPARATION, HANDLING, AND STORAGE

Refer to the Laboratory Manual for the central laboratory.

7.2.4 SPECIMEN SHIPMENT

Refer to the Laboratory Manual for the central laboratory.

7.3 STUDY SCHEDULE

7.3.1 SCREENING/ENROLLMENT

Visit 1E

Visit 1E should occur at the subject's parent-study EOS visit, with a window of + 6 weeks.

Collection of NSAID/acetaminophen usage, physical and knee examination, weight measurement, vital sign measurements, and venipuncture and collection of samples for clinical laboratory tests and biomarker analysis will be performed at the parent-study Week 56 (EOS) visit and therefore do not need to be repeated at Visit 1E.

The Investigator or designee must explain the nature of the study protocol and associated risks to the potential study participant. The potential participant must be allowed to review the study information and to ask questions before being asked to sign and date the ICF. Written informed consent must be provided, signed, and dated by the potential study participant prior to initiation of any screening evaluations or other study-related procedures. The signature, date, and the name of the individual at the site who obtained the informed consent will be recorded. Subjects will retain the same subject number as assigned in the parent study.

Subjects who sign the ICF at Visit 1E will be considered consented. For WOCBP, a urine-based pregnancy test will then be performed.

After the subject is deemed eligible for the study based on inclusion/exclusion criteria, the following procedures and assessments will be performed at Visit 1E:

- PASS assessment
- Pain NRS assessment
- Collection of AE and concomitant procedures/therapies/medication data
- IA injection of study medication by the Unblinded Investigator (injector) into the target knee; **the target knee must be the same as the knee injected in the parent study.**

Investigators will maintain a confidential log of all subjects who have been screened for participation in the study whether or not the subject was eligible for study participation.

7.3.2 STUDY VISITS

Visit 2E

Visit 2E should occur 24 weeks after the Visit 1E injection with a window of \pm 4 weeks.

Confidential

The following procedures and assessments will be performed at Visit 2E:

- Pain NRS assessment
- WOMAC questionnaire
- Collection of AE and concomitant procedures/therapies/medication data
- Assessment of NSAID/acetaminophen usage
- Knee examination
- Weight measurement
- Vital sign measurements (pulse rate and blood pressure)
- Venipuncture and collection of samples for clinical laboratory tests
- Radiograph – bilateral in weight-bearing fixed flexion position, PA view X-ray

Visit 3E

Visit 3E should occur 48 weeks after the Visit 1E injection with a window of ± 4 weeks. Subjects should fast for 8 hours prior to this visit.

The following procedures and assessments will be performed at Visit 3E:

- Pain NRS assessment
- WOMAC questionnaire
- PASS assessment
- SF-36
- Collection of AE and concomitant procedures/therapies/medication data
- Assessment of NSAID/acetaminophen usage
- Pregnancy test (urine-based) in WOCBP
- Physical examination
- Knee examination
- Weight measurement
- Vital sign measurements (temperature, pulse rate, and blood pressure)
- Venipuncture and collection of samples for clinical laboratory tests and biomarkers
- Radiograph – bilateral in weight-bearing fixed flexion position, PA view X-ray
- IA injection of LOR into the target knee; **the target knee must be the same as the knee injected in the parent study.**

Visit 4E (Phone Visit)

The Visit 4E phone visit should occur on Week 52 (with a window of ± 7 days). Sites will contact subjects to collect AE and concomitant procedures/therapies/medication data.

Visit 5E, 7E, 9E, etc.

These visits should occur on Weeks 74, 126, 178, etc. with a window of ± 4 weeks.

The following procedures and assessments will be performed at these visits:

- Pain NRS assessment
- WOMAC questionnaire
- Collection of AE and concomitant procedures/therapies/medication data
- Assessment of NSAID/acetaminophen usage
- Knee examination
- Radiograph – bilateral in weight-bearing fixed flexion position, PA view X-ray

Visit 6E, 8E, 10E, etc.

These visits should occur on Weeks 100, 152, 204, etc. with a window of ± 4 weeks.

The following procedures and assessments will be performed at these visits:

- Pain NRS assessment
- WOMAC questionnaire
- PASS assessment
- SF-36
- Collection of AE and concomitant procedures/therapies/medication data
- Assessment of NSAID/acetaminophen usage
- Pregnancy test (urine-based) in WOCBP
- Knee examination
- Weight measurement
- Vital sign measurements (temperature, pulse rate, and blood pressure)
- Venipuncture and collection of samples for clinical laboratory tests
- Radiograph – bilateral in weight-bearing fixed flexion position, PA view X-ray
- IA injection of LOR into the target knee; **the target knee must be the same as the knee injected in the parent study.**

